2 STUDY OBJECTIVES

2.1 Primary Objective

Primary Objective:	Outcome Measure:
To examine the tumour genetic and proteomic profile at the point of disease progression in patients receiving osimertinib as first-line EGFR TKI therapy for EGFRm+ locally advanced or metastatic NSCLC compared to the profile prior to initiation of treatment	Proportion of patients with a given tumour genetic and proteomic marker (including, but not limited to, EGFR mutations, human epidermal growth factor receptor 2 [HER2], and proto-oncogene encoding hepatocyte growth factor receptor [cMET] expression and/or amplification) at the point of disease progression as defined by the Investigator; the choice of markers is dependent on the profile comparison at the point of disease progression and prior to treatment initiation

2.2 Secondary Objectives

Secondary Objectives:	Outcome Measures:
To assess the efficacy of osimertinib as first-line EGFR TKI therapy for patients with EGFRm+ locally advanced or metastatic NSCLC	PFS, according to RECIST 1.1 by Investigator assessment, and other selected clinical efficacy endpoints including: 
• ORR• DoR• DCR
To assess the efficacy of osimertinib in patient subgroups defined by molecular profile, including but not limited to: 
• EGFR Ex19del or L858R mutation• EGFR Ex19del or L858R detectable in plasma-derived circulating tumour deoxyribonucleic acid (ctDNA)	PFS, according to RECIST 1.1 by Investigator assessment, and other selected clinical efficacy endpoints including: 
• ORR• Tumour shrinkage/depth of response, defined as best change from baseline in target lesion tumour size• Time to treatment discontinuation or death (TTD)• Important patient and disease characteristics
To further assess the efficacy of osimertinib post-progression	
• TTD• Time to first subsequent therapy or death (TFST)

2.3 Safety Objective

Safety Objective:	Outcome Measures:
To summarise the safety and tolerability profile of osimertinib as first-line EGFR TKI therapy for patients with EGFRm+ locally advanced or metastatic NSCLC	
• AEs graded by Common Terminology Criteria for Adverse Events (CTCAE) version 4.0• Clinical chemistry, haematology and urinalysis• Vital signs, physical examination, body weight• Electrocardiogram (ECG)• World Health Organization (WHO) performance status

2.4 Exploratory Objective

Exploratory Objective:	Outcome Measures:
CCI	CCI

3 PATIENT SELECTION, ENROLMENT, RESTRICTIONS, DISCONTINUATION AND WITHDRAWAL

Male and female patients aged 18 years and over with locally advanced or metastatic pathologically confirmed adenocarcinoma of the lung, not amenable to curative surgery or radiotherapy. Patients will have a tumour that harbours one of the EGFR mutations known to be associated with EGFR TKI sensitivity, either alone or in combination with other EGFR mutations (EGFR mutation status determined by a local laboratory). Patients must be EGFR TKI treatment-naïve and eligible to receive first-line treatment with osimertinib.

Each patient should meet all of the inclusion criteria and none of the exclusion criteria for this study. Under no circumstances can there be exceptions to this rule.

3.1 Inclusion Criteria

For inclusion in the study patients should fulfil the following criteria:

1. Provision of informed consent prior to any study specific procedures (signed and dated Informed Consent Form).
2. Patients aged 18 years or older (specific age may vary according to country regulations for legal age).

3. Patients with histological confirmation of locally advanced or metastatic, non-squamous NSCLC who are not candidates for local curative treatment.
4. Patients with M1 stage according to the Tumour, Node, and Metastasis Classification of Malignant Tumours (TNM) version 7 including M1a (malignant effusion) or M1b (distant metastasis), or locally advanced disease that is not a candidate for curative treatment (including patients who progress after chemo-radiotherapy in stage III disease).
5. Patients with an EGFR deletion or mutation known (from tumour biopsy or plasma) to be associated with EGFR TKI sensitivity before treatment assessed by a local laboratory certified by Clinical Laboratory Improvement Amendments (USA sites) or an accredited local laboratory (sites outside of the USA).
6. Existence of measurable or evaluable disease (as per RECIST 1.1 criteria).
7. Possibility of obtaining sufficient tissue sample, via a biopsy or surgical resection of the primary tumour or metastatic tumour tissue, within the 60 days prior to study entry and at or after RECIST 1.1-defined progression. An archival biopsy is acceptable as long as there has been no intervening anticancer treatment since the time the biopsy was obtained to enrolment in this clinical study and as long as it was within 60 days of study entry. A sufficient tissue sample would consist of formalin-fixed, paraffin-embedded tumour tissue blocks, or at least 15 re-cut unstained sections from formalin-fixed paraffin-embedded tumour tissue block, presented on slides. Each section should be 5 μm thick.
8. WHO performance status 0-1.
9. Life expectancy \geq 12 weeks.
10. Capacity to swallow.
11. Patients able to complete study and within geographical proximity allowing for adequate follow-up.
12. Resolution of all acute toxic effects of previous anticancer therapy (which can only be adjuvant or neoadjuvant) or surgical interventions to Grade 1 according to the National Cancer Institute (NCI) CTCAE version 4.0 (except for alopecia or other side effects that the Investigator does not consider to be a risk to patient safety).
13. Female patients must be using highly effective contraceptive measures, and must have a negative pregnancy test prior to start of dosing if of childbearing potential or must have evidence of non-childbearing potential by fulfilling one of the following criteria at screening:

- Postmenopausal defined as aged 50 years or more and amenorrhoeic for at least 12 months following cessation of all exogenous hormonal treatments.
- Women under 50 years old would be considered postmenopausal if they have been amenorrhoeic for 12 months or more following cessation of exogenous hormonal treatments and with luteinising hormone and follicle -stimulating hormone levels in the postmenopausal range for the institution.
- Documentation of irreversible surgical sterilisation by hysterectomy, bilateral oophorectomy or bilateral salpingectomy but not tubal ligation.

14. Male patients must be willing to use barrier contraception (see Restrictions, Section [3.5](#)).

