3.2 Exclusion Criteria

Patients should not enter the study if any of the following exclusion criteria are fulfilled:

1. Locally advanced lung cancer candidate for curative treatment through radical surgery and/or radio(chemo)therapy.
2. Patients diagnosed with another lung cancer subtype, patients with mixed NSCLC with predominantly squamous cell cancer, or with any small cell lung cancer component.
3. Patients with an EGFR exon 20 insertion.
4. Patients with just one measurable or evaluable tumour lesion that has been resected or irradiated prior to their enrolment in the study.
5. Second active neoplasia.
6. Treatment with an investigational drug within five half-lives of the compound.
7. Participation in another clinical study with an IP during the last 3 weeks before the first day of study treatment.
8. Patients who have received prior immunotherapies.
9. Patients who have received prior EGFR treatments for lung cancer.
10. Patients who have received prior treatment with an EGFR TKI including in the adjuvant setting.
11. Patients who have received previous treatment for metastatic or stage IV disease.

12. Prior treatment with cytotoxic chemotherapy for advanced NSCLC (neoadjuvant/adjuvant chemotherapy is permitted if at least 6 months have elapsed between the end of chemotherapy and the first day of study treatment).
13. Patients with a history of cancer that has been completely treated, with no evidence of malignant disease currently cannot be enrolled in the study if their chemotherapy was completed less than 6 months prior and/or have received a bone marrow transplant less than 2 years before the first day of study treatment.
14. Any unresolved toxicities from prior therapy greater than CTCAE Grade 1 at the time of starting study treatment with the exception of alopecia and Grade 2, prior platinum-therapy related neuropathy.
15. Any evidence of severe or uncontrolled systemic diseases, including uncontrolled hypertension and active bleeding diatheses, which in the Investigator's opinion makes it undesirable for the patient to participate in the trial or which would jeopardise compliance with the protocol, or active infection (eg, patients receiving treatment for infection) including hepatitis C and human immunodeficiency virus (HIV), or active uncontrolled Hepatitis B virus (HBV) infection.
 - Screening for chronic conditions is not required.

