^b Values determined from comprehensive review (internal to AZ) of each compound's PK half-life and determination of the washout period.

^c Estimated value as PK of arsenic trioxide has not been studied.

AZ = AstraZeneca; PK = pharmacokinetics; TdP = Torsades de Pointes.

E 3 Other TdP risk categories

Patients receiving drugs that prolong QT interval or may increase the risk of TdP from other TdP risk categories can be enrolled, notwithstanding other exclusions and restrictions, if these drugs are considered essential for patient management and the patient has been stable on therapy. Close monitoring of ECGs and electrolytes is recommended.

Patients with **congenital long QT syndrome** are excluded from this study.

During study treatment and for a period of 2 weeks after discontinuing study treatment, if it is considered essential for patient management to co-administer drugs known to prolong QTc interval, **regardless of TdP risk category**, close monitoring of ECGs and electrolytes is recommended.

Appendix F Guidelines for Evaluation of Objective Tumour Response Using RECIST 1.1 Criteria (Response Evaluation Criteria in Solid Tumours)

F 1 Introduction

This appendix details the implementation of RECIST 1.1 guidelines ([Eisenhauer et al 2009](#)) for the D5161C00003 study with regards to Investigator assessment of tumour burden including protocol-specific requirements for this study.

F 2 Definition of Measurable, Non-Measurable, Target and Non-Target Lesions

Only patients with measurable disease at baseline should be included in the study. Measurable disease is defined by the presence of at least one measurable lesion which has not been previously irradiated and not chosen for biopsy during the Screening Period.

Measurable:

A lesion, not previously irradiated and not chosen for biopsy during the Screening Period, that can be accurately measured at baseline as ≥ 10 mm in the longest diameter (except lymph nodes which must have short axis ≥ 15 mm) with CT or MRI and which is suitable for accurate repeated measurements. If only one measurable lesion exists, it is acceptable to be used (as a target lesion) as long as it has not been previously irradiated and baseline tumour assessment scans are done at least 14 days after the screening biopsy is performed.

Non-measurable:

- All other lesions, including small lesions (longest diameter < 10 mm or pathological lymph nodes with ≥ 10 to < 15 mm short axis at baseline*)

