F 4.5 Symptomatic Deterioration

Symptomatic deterioration is not a descriptor of an objective response: it is a reason for stopping study therapy.

Patients with 'symptomatic deterioration' requiring discontinuation of treatment without objective evidence of disease progression at that time should continue to undergo tumour assessments where possible until objective disease progression is observed.

F 4.6 Evaluation of Overall Visit Response

The overall visit response will be derived using the algorithm shown in [Table F4](#).

Table F4 Overall Visit Response

Target lesions	Non-target lesions	New lesions	Overall response
CR	CR	No	CR
CR	NA	No	CR
CR	Non-CR/Non-PD	No	PR
CR	NE	No	PR
PR	Non-D or NE	No	PR
SD	Non-PD or NE	No	SD
NE	Non-PD or NE	No	NE
PD	Any	Yes or No	PD
Any	PD	Yes or No	PD
Any	Any	Yes	PD

CR = complete response, PR = partial response, SD = stable disease, PD = progressive disease, NE = not evaluable, NA = not applicable (only relevant if there were no NTLs at baseline).

F 5 References

Eisenhauer et al 2009

Appendix G Definition of Women of Childbearing Potential and Highly Effective Contraceptive Methods

Definition of Women of Childbearing Potential

Women of Childbearing Potential (WOCBP):

Women between menarche and menopause who have not been permanently or surgically sterilised and are capable of procreation.

Women NOT of Childbearing Potential:

Women who are permanently or surgically sterilised or postmenopausal (definitions below):

Permanent sterilisation includes hysterectomy and/or bilateral oophorectomy and/or bilateral salpingectomy but excludes bilateral tubal occlusion. Tubal occlusion is considered a highly effective method of birth control but does not absolutely exclude possibility of pregnancy. (The term occlusion refers to both occluding and ligating techniques that do not physically remove the oviducts).

- Women who have undergone tubal occlusion should be managed on trials as if they are of WOCBP (eg, undergo pregnancy testing, as required by the study protocol)
- Women will be considered postmenopausal if they are amenorrhoeic for 12 months without an alternative medical cause. The following age-specific requirements apply:

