PD	At least a 20% increase in the sum of the diameters of TLs, taking as reference the smallest sum on study (this includes the baseline sum if that is the smallest on the study). In addition to the relative increase of at least 20%, the sum must also demonstrate an absolute increase of at least 5 mm.
NE	Only relevant if any of the TLs were not assessed or not evaluable or had a lesion intervention at this visit. Note: If the sum of diameters meets the progressive disease criteria, progressive disease overrides not evaluable as a TL response.
NA	No TLs are recorded at baseline.

Abbreviations: CR = Complete response; NA = Not applicable; NE = Not evaluable; PD = Progressive disease; PR = Partial response; SD = Stable disease; TL = Target lesion.

Rounding of TL data

For calculation of PD and PR for TLs, percentage changes from baseline and previous minimum should be rounded to one decimal place before assigning a TL response. For example, 19.95% should be rounded to 20.0% but 19.94% should be rounded to 19.9%.

Missing TL data

For a visit to be evaluable, all TL measurements should be recorded. However, a visit response of PD should still be assigned if any of the following occurred:

- A new lesion is recorded.
- A NTL visit response of PD is recorded.
- The sum of TLs is sufficiently increased to result in a 20% increase, and an absolute increase of ≥ 5 mm, from nadir (defined below) even assuming the non-recorded TLs have disappeared.

The nadir (ie, the smallest measurement based on the same set of lesions at baseline and on a given visit) can only be taken from assessments where all the TLs had a longest diameter (LD) recorded.

Lymph nodes

For lymph nodes, if the size reduces to <10 mm, these are considered non-pathological.

However, a size will still be measured, and this size should still be used to determine the TL visit response as normal. In the special case where all lymph nodes are <10 mm and all other TLs are 0 mm, then although the sum may be >0 mm, the calculation of TL response should be overwritten as a CR.

TL visit responses subsequent to CR

A CR response can only be followed by CR, PD or NE. If a CR has occurred, then the following rules at the subsequent visits must be applied:

- Step 1: If all lesions meet the CR criteria (ie, 0 mm or <10 mm for lymph nodes), the response will be set to CR irrespective of whether the criteria for PD of TL is also met for lymph node (ie, if a lymph node LD increases by 20% but remains <10 mm).

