3.2.2.4 Disease control rate

Disease control rate (DCR) is defined as the percentage of patients who have a best overall response of complete response or partial response or stable disease at ≥ 8 weeks. Patients must have lesions (either TLs or NTLs) recorded at baseline to be included in the denominator. The 8-week time point will allow for a visit window and be defined as on or after study day 49 (allowing for the visit window).

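### Eligibility text conflicts on measurable disease, and if patients without target lesions were treated, SAP 3.2.2.2 and 4.2.9.3 give different ORR denominators

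*Protocol*

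**What the plan says.** **Eligibility.** Protocol 3.1, criterion 6: "Existence of measurable or evaluable disease (as per RECIST 1.1 criteria". Protocol 3.2, exclusion 4, also treats the two terms as alternatives: "Patients with just one measurable or evaluable tumour lesion that has been resected or irradiated prior to their enrolment in the study". The opening of Protocol Section 3 makes the lists binding: "Each patient should meet all of the inclusion criteria and none of the exclusion criteria for this study".

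**RECIST appendix and SAP.** Protocol Appendix F 2 says "Only patients with measurable disease at baseline should be included in the study" and continues "Measurable disease is defined by the presence of at least one measurable lesion which has not been previously irradiated", also ruling out lesions chosen for the screening biopsy, with an exception for a sole measurable lesion. SAP 3.1.1 repeats the measurable-only sentence.

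**Patients without target lesions.** The SAP has rules for them. Table 4 has a not-applicable category described as "No TLs are recorded at baseline". Table 5 has a note for such patients, and Table 6 has four rows with target lesions not applicable. For DCR, SAP 3.2.2.4 says "Patients must have lesions (either TLs or NTLs) recorded at baseline to be included in the denominator". Protocol Table F4 has no row specific to them; its footnote reads "NA = not applicable (only relevant if there were no NTLs at baseline", so the term there covers only absent non-target lesions.

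**ORR denominator.** SAP 3.2.2.2 uses all treated patients with a measurable lesion at baseline. SAP 4.2.9.3 uses full-analysis-set patients with any evidence of disease at baseline.

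**The concern.** A patient with evaluable but non-measurable disease passes criterion 6 and fails the sentence in Appendix F 2 and SAP 3.1.1. Such a patient is plausible. Criterion 4 names malignant effusion, and Appendix F 2 classes effusions, bone lesions, brain metastases, previously irradiated lesions and nodes of 10 to under 15 mm as non-measurable. A patient with an effusion and a biopsied 12 mm node would be one case. Neither document defines evaluable to mean measurable.

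The response endpoints are at stake. If every patient had measurable disease, the two ORR denominators would coincide and the difference in wording would be harmless. Under criterion 6 they need not coincide, and nothing in the SAP says which applies. Under SAP Table 6 a patient without target lesions can be CR, SD, PD or NE but never PR. Best percentage change in tumour size (SAP 3.2.2.7) does not exist for that patient.

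**Working it through.** The plan states no figure that depends on this rule, so there is none to reproduce. The check compares the texts and then illustrates the effect on ORR.

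**Step 1. Which populations the texts admit**

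| Text | Measurable lesion | Non-target lesions only |
|---|---|---|
| Protocol 3.1 criterion 6 | yes | yes, if evaluable |
| Protocol Appendix F 2 | yes | no |
| SAP 3.1.1 | yes | no |
| SAP Tables 4 to 6 | rules given | rules given |
| DCR denominator, SAP 3.2.2.4 | in | in |
| ORR denominator, SAP 3.2.2.2 | in | out |
| ORR denominator, SAP 4.2.9.3 | in | in |

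The last two rows disagree only in the final column. The conflict therefore changes a result only if such patients were treated.

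**Step 2. Inputs for the illustration**

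- N = 150, the planned enrolment (Protocol synopsis and 8.2).
- Response rate in measurable patients 77%, the first-line rate cited in Protocol 1.1 for 60 patients in the AURA expansion cohorts.
- Share f with non-measurable disease only: not in the documents; assumed 0, 5, 10 and 15%.
- No responders among non-measurable patients: assumed.

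**Step 3. Formulas**

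k = 150 × f, m = 150 − k, r = 0.77 × m, each rounded to whole patients (7.5 taken as 8, 22.5 as 22). ORR under 3.2.2.2 is r/m; under 4.2.9.3 it is r/150. Intervals are exact 95%.

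| f | k | SAP 3.2.2.2 | SAP 4.2.9.3 | Gap (points) |
|---|---|---|---|---|
| 0% | 0 | 116/150 = 77.3% (69.8–83.8) | 116/150 = 77.3% (69.8–83.8) | 0 |
| 5% | 8 | 109/142 = 76.8% (68.9–83.4) | 109/150 = 72.7% (64.8–79.6) | 4.1 |
| 10% | 15 | 104/135 = 77.0% (69.0–83.8) | 104/150 = 69.3% (61.3–76.6) | 7.7 |
| 15% | 22 | 99/128 = 77.3% (69.1–84.3) | 99/150 = 66.0% (57.8–73.5) | 11.3 |

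**Step 4. Why these are the largest gaps for each share**

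SAP Table 6 allows CR without target lesions, so some of the k patients could respond. If all of them did, the 4.2.9.3 figure at 10% would be (104 + 15)/150 = 79.3%, which is 2.3 points above 77.0% instead of 7.7 below. At 5% it would be 117/150 = 78.0% (1.2 above) and at 15% 121/150 = 80.7% (3.3 above). The no-responder case is the wider of the two extremes at each share.

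**Step 5. Primary endpoint**

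The pair calculation, 103 × 0.7 × 0.7 = 50.5, and the precision table for 50 pairs contain no term for measurability. The primary analysis set (Protocol 8.3.1, SAP 2.1.1) is defined by paired biopsies and investigator-assessed progression.

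**The case against.** The best defence is that the documents show which text decides eligibility. Protocol 3.3 sends investigators to Sections 3.1 and 3.2, and Appendix F presents itself as guidance on assessing tumour burden. SAP 2.2 defines an eligibility deviation by the inclusion and exclusion criteria. All of this stands, and it rules out several stronger readings that a reader might infer:

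- *Sites enrolled different populations, or the same patient is a deviation under one text and not the other.* A patient who meets criterion 6 as written is not an eligibility deviation under SAP 2.2, and no site is told to take eligibility from Appendix F.
- *A countable group was wrongly enrolled.* Any count needs a proportion that the documents do not give. Criterion 7 and Protocol 5.3.1 require adequate tissue and bar bone-metastasis and cytology samples, which narrows the group; it may be empty.
- *The protocol gives these patients no visit response.* Table F4 still assigns PD through its rows for any target-lesion status. Only CR, SD and NE are missing, and SAP Table 6 supplies them.
- *The not-applicable rows prove that such patients were expected.* One of the four, which gives no evidence of disease, describes a patient with no lesions at all, whom criterion 6 also bars. The rows may simply be exhaustive programming rules, needed in any case because the full analysis set holds every treated patient.
- *The range of progression patterns profiled is narrowed.* Neither document links measurability to resistance pattern.

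It can also be said that SAP 3.2.2.2 already restricts ORR to measurable disease, so the response population is settled. That part fails, because SAP 4.2.9.3 gives a wider denominator for the same endpoint.

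**Conclusion.** The contradiction is explicit, in current text of both documents, and not an artefact of the amendment history. Protocol 3.1 and 3.2 admit measurable or evaluable disease; Appendix F 2 and SAP 3.1.1 admit measurable disease only. Enrolment, the deviation listing and the primary endpoint do not turn on it.

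The result that can turn on it is ORR, through the two SAP denominators. The size is zero if every treated patient had measurable disease. Under the assumptions above it is at most 4.1, 7.7 and 11.3 percentage points at non-measurable shares of 5, 10 and 15%. Those shares and the absence of responders are assumptions, and the 77% is borrowed from an earlier cohort. That the denominators differ is certain; how far the estimates differ cannot be known from the documents. DCR is not affected in this way, since both SAP sections on it accept patients with non-target lesions only.

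**What to change.** 1. Make the sentence in Appendix F 2 and SAP 3.1.1 agree with criterion 6, the text that Protocol 3.3 points to. If the sponsor prefers to reconcile the passages otherwise, criterion 6 and exclusion 4 would have to change and patients already treated would have to be accounted for.
2. State one ORR denominator, in the same words, in SAP 3.2.2.2 and 4.2.9.3.
3. Add to Protocol Table F4 the three SAP Table 6 rows for patients with non-target lesions only (CR, SD and NE), and widen the footnote so that not applicable also covers absent target lesions. The no-evidence-of-disease row should not be copied.
4. Report the number of full-analysis-set patients with no target lesion at baseline beside ORR and best change in tumour size.

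SAP 2.2 needs no added sentence. The cost is wording in one appendix and two or three SAP paragraphs, three table rows and one baseline count. No new data are needed. The change cannot alter who was enrolled, since Protocol version 7.0 is dated April 2023 with study end by Q2 2023, but it fixes what the reported response rates describe.
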